### 5.6.3 MINIMIZING PARTICIPANT BURDEN

We have designed the study to minimize participant burden. The option of home study visits will be provided for participants enrolled at the JHU site, which we expect will increase recruitment yield by making the study more convenient for participants. We will initially conduct home study visits during weekdays and daylight hours, but may consider weekend visits if needed to

increase enrollment rate. If participants report challenges making it to the research clinic site for follow-up visits due to scheduling conflicts, we will consider adding non-business and weekend hours to accommodate participant's schedules as much as possible. After a participant is enrolled in the study, research staff will be expected to follow our Difficult to Reach Protocol (Section 5.6.5). All attempts to contact, including the failed attempts and the outcome of the attempts, will be documented in the electronic case report form. A copy of the letter(s) sent to the participants will be saved in the case report form.

## 5.6.4 STUDY PARTICIPANT INFORMATIONAL RESOURCES

### 5.6.4.1 STUDY PARTICIPANT WEBSITE

A study resource webpage will be provided to study participants at the following URL:

<https://www.[name].com/study-participants>

Access to the study participant website will require a password , which will be provided to the study participant at the baseline visit by the study coordinator. This website is intended to provide reference materials regarding study schedule of activities and procedures to simplify the process for our study participants. No data will be collected from study participants through this website.

### 5.6.4.2 STUDY PARTICIPANT INSTRUCTION GUIDE

A study participant manual (replicating content from the study participant website) will also be provided to participants at the baseline visit. This is intended to provide important contact information and reference materials regarding study schedule of activities.

## 5.6.5 DIFFICULT TO REACH PROTOCOL

A total of 10 contact attempts are made to all the phone numbers provided by the participant at varying times of the day. The calls may be divided in the following manner: 2 calls before 11 AM, 2 calls between 11 AM and 3 PM, 2 calls between 3 PM and 6 PM, 2 calls after 6 PM, and 2 calls on the weekend.

- a) At least 5 text messages are sent.
- b) At least 5 emails are sent – if email provided.
- c) One “unable to contact letter” is sent to the home address. The letter must contain name and address of the participant, visit, compensation amount, date, name and contact information of the study team member.
- d) Attempt to contact 1-3 alternative contact(s); defined for the participant as ‘someone who will know how to reach you.’

## 5.6.6 POTENTIAL PROBLEMS AND ALTERNATIVE STRATEGIES

If the pace of recruitment is below the target goal of 13-14 participants per month, we will pursue the following strategies to increase recruitment:

- a) If accrual is limited by lack of resources for screening (i.e. insufficient research coordinator effort one or both recruitment sites), we will reallocate resources accordingly to ensure that there is sufficient resource coordinator time and effort available to screen and enroll interested participants.
- b) If accrual is limited by lack of interested participants, we will consult experts in the ICTR for advice regarding alternative recruitment strategy methods. We could consider, for example, advertisements on buses, radio, or other online sites if appropriate based on the advice of our local recruitment experts. We could consider addition of another recruitment site if allowable per study budget, or if accrual is significantly below target, we could request a budget supplement to include an additional site.

c) If accrual is limited by eligibility criteria, we will consider modifying the eligibility criteria to be less restrictive without compromising the validity of the study findings.

## 6 STUDY INTERVENTION

### 6.1 STUDY INTERVENTION DESCRIPTION

Participants randomized to the dDPP will receive the Sweetch digital health kit (app log in instructions and Bluetooth-enabled digital scale) within 8-12 days via mail. The rationale for mailing the digital health kit is to allow participants to obtain baseline PA measurements prior to starting the intervention, and also to replicate the real-world experience in which there would likely be some delay between prescriber ordering of the dDPP and patient receipt of the product.

The referral process to the Sweetch dDPP will be generated in a RedCap database, with an automated email sent to Sweetch Health, Ltd. The RedCap referral will include the following participant identifiers at the time of the referral:

[figure not shown]
- First Name
- Last Name
- Email Address
- Phone Number
- Baseline Weight
- Baseline BMI
- Laboratory measure(s) that rendered the participant eligible for the DPP (A1C, fasting glucose, plasma glucose after 75 gram OGTT) and date of the relevant lab result(s)

This will allow the Sweetch support team to contact the participant directly in the event that the user has any technical difficulties installing the app and/or syncing the Bluetooth enable digital body weight scale. A maximum of 5 communication attempts will be made directly by Sweetch to register the participant in the app. Baseline weight, BMI, and A1C data are provided to the dDPP arm as this information is also required for referral to the hDPP arm.

[figure not shown]
The Sweetch app uses self-tracking and multiple evidence-based persuasive eCoaching strategies, which have been described in detail in a recent review of automated technologies seeking to promote behavioral change. Notably, not only does the app itself employ multiple persuasive systems design elements, but the adaptive push notifications do as well: reduction (breaking down goals into smaller goals), tunneling (guiding user step by step), tailoring, personalization (continuously tuning goals and messages based on past real-world compliance and capabilities), simulation, praise, reminders, suggestion, competition, recognition, education and goal-setting.

The Sweetch AI algorithm is used in several app components to deliver just-in-time support and/or adapt recommendations or goals in real-time based on the user's response. For example, push notifications will be sent when the algorithm detects that the user is potentially available and able to act upon the recommendation, based on various parameters including location, previous response, calendar availability, and weather, etc. These tailored pushed notifications motivate participants to meet the PA goal of 150 minutes per week, lose 5% of body weight, monitor meals and drinks, and complete the 19 CDC in-app diabetes prevention lessons for the core phase (months 1-6) and 6 in-app lessons for the core maintenance phase (months 7-12). A maximum of 10 push notifications will be sent per day; however, participants who are meeting their goals may not receive any notifications on a given day. In some instances, notifications/reminders will be sent via email mainly for educational content and technical support. For example, an email will be sent to participants upon referral to the dDPP providing the user a link to download the Sweetch app and instructions on how to complete the registration process. Also, for some participants, emails may be sent to supplement the education provided via the in-app lessons. Participants will be able to turn off/on push notifications at any time within the Sweetch app, but will not be able to make modifications to the frequency or timing of the notifications as these are generated using AI technology and are continuously adapted based on the participant's behavioral patterns and progress in the program.

[figure not shown]
This screenshot shows an example of the Sweetch personalized push notification, and home screen with goal tracking (PA, weight, in-app lessons, and habits):

This screenshot shows the main page of the app and the T2D Prevention Lessons based on the CDC curriculum. Participants are reminded to take the in-app lessons:

This screenshot shows the participant achievements, a form of social support:

## 6.2 CONTROL ARM DESCRIPTION

Participants randomized to the hDPP arm will be provided a list of participating CDC recognized lifestyle change programs within a 25 mile radius of the main study site. Eligible programs will be identified using the CDC's Recognized Lifestyle Change Program Website, which maintains a registry of recognized programs.

For this trial, eligible local programs must meet the following criteria:

- Have preliminary or full recognition status by the CDC (i.e. identifiable on the CDC's online registry)
- Provide in-person or *synchronous* distance learning (video conferencing) modalities
- Expressed interest in participating in the clinical trial
- Agree to share outcomes and attendance data (per CDC reporting requirements) using study team's electronic data capture form.

To achieve preliminary or full recognition, local DPPs must adhere to the CDC's Diabetes Prevention Recognition Program Standards and Operating Procedures. Sessions are delivered by trained lifestyle coaches and each site offers at least 16 sessions during the first 6 months (core phase) and 6 sessions during the last 6 months (core maintenance phase). Each program follows a CDC approved curriculum, using either the 2012 National DPP curriculum or the more recent CDC-developed PreventT2 curriculum (majority). Core sessions are held weekly for months 0-6, then typically bi-monthly for the core maintenance sessions in months 7-12, which is divided into two intervals (months 7-9 and months 10-12). Programs are required to offer at least 6 sessions during the last 6 months (3 per interval).

The CDC recognizes several modalities for DPP, including in-person, distance learning, and online. Distance learning refers to both synchronous and asynchronous delivery using video and phone conferencing. In **synchronous** delivery, instruction is conducted in real time. That is, all participants are present at the same time. Synchronous delivery most closely resembles a traditional classroom, despite the participants being located remotely. It requires an organized timetable and an instructor to be present. Participants can typically interact with the instructor and they may even interact with each other. In **asynchronous** delivery, instruction is self-paced. Participants access course materials on their own schedules and are not required to be together at the same time. Delivery technology includes video and audio recordings, discussion board forums, e-mail, and self-directed print materials. Hybrid, or blended, learning is when synchronous and asynchronous technologies are combined.

Among these CDC-recognized delivery modalities, for participants randomized to receive the hDPP, local DPPs will only be permitted to use in-person, **synchronous** distance learning, or combined modality to avoid contamination with the dDPP intervention. The online only modality will not be permitted. Online platforms often use wireless weight tracking, PA trackers, and social support and engagement tools that would introduce contamination with the study intervention. In addition, *asynchronous* distance learning will not be permitted as it will be practically challenging to track participant engagement in these programs. However, a combination of asynchronous and synchronous distance learning will be permitted if we are able to capture all the "attendance" data.

Eligible programs have been identified from a search of the CDC National Diabetes Program website and the state department of health websites for Maryland and Pennsylvania. The in-person delivery of these local DPPs occurs in various settings (hospital outpatient, primary care, community, church). Programs may use any video conferencing platform (e.g. Zoom, WebEx, Google Meet) to deliver synchronous distance learning. If additional DPP programs meeting our eligibility criteria are identified after study initiation, they will be approached by the study team for inclusion in the trial.

COVID-19 has introduced significant challenges in the delivery of in-person DPP, and the majority of local DPPs have transitioned nearly entirely to distance learning through the use of video conferences. Since programs enroll cohorts at different frequencies on a rolling basis, participants will be informed that once they initiate in a program, they will need to continue in that program at least through the duration of the core phase (months 1-6), after which they may switch to an alternative hDPP. However, participants will be encouraged to complete the full program at the same hDPP.

For participants expressing interest in a distance learning DPP, the study team will refer the participant to the program with the earliest availability. For participants expressing interest in in-person DPP, the study team will refer the participant to the closest program that is closest to their home and has the earliest availability. The referral process will be generated in RedCap, with an

automated email sent to the local DPP coordinator. The RedCap referral will include the following participant identifiers at the time of the referral:

- First Name
- Last Name
- Email Address
- Phone Number
- Baseline Weight
- Baseline BMI
- Laboratory measure(s) that rendered the participant eligible for the DPP (A1C, fasting glucose, plasma glucose after 75 gram OGTT) and date of the relevant lab result(s)

Local DPPs will then initiate outreach as part of their normal protocols. We will advise local DPPs that a maximum of 5 attempts should be made to reach our study participants for enrollment in their programs.

## 6.3 PREPARATION/HANDLING/STORAGE/ACCOUNTABILITY

### 6.3.1 ACQUISITION AND ACCOUNTABILITY

Sweetch Health, Ltd. will provide the Sweetch app, digital scales, instructional materials, technical support for participants, hosting of the app, and sharing of all app system usage data with the study team.

### 6.3.2 FORMULATION, APPEARANCE, PACKAGING, AND LABELING

The Sweetch digital health kit will consist of the Sweetch app and Bluetooth enabled digital scale. The scale will be packaged in a branded white box with the Sweetch logo. A user manual will be provided with the scale.

### 6.3.3 PRODUCT STORAGE AND STABILITY

The Sweetch health kit will be stored in a locked office at room temperature. With the exception of informational materials, there are no products to be provided to control participants.

This study will be using various A1C testing devices, all of which are FDA approved and certified according to NGSP (National Glycohemoglobin Standardization Program) standards. The A1C testing devices include the Afinion™ 2 Analyzer, Siemens DCA Vantage, and A1CNow®+ test kits (Professional Multi-test HbA1C System; Polymer Technology System, Inc., Indianapolis, IN). All test kits and control solutions will be stored according to manufacturer's instructions. A log will be maintained to ensure that kits are used prior to expiration date. Any expired test kits will be discarded.

## 6.4 MEASURES TO MINIMIZE BIAS: RANDOMIZATION AND BLINDING

Block stratified randomization by baseline A1C level (5.7% to 6.0% vs. 6.1% to 6.4%) and recruitment site (JHU vs. Reading) will be done to ensure that the groups are balanced with respect to this variable, since higher A1C level at baseline is the strongest risk factor for progression to incident diabetes and potential need for glucose-lowering medications.

For several pragmatic reasons, this will be an open-label trial (i.e. treatment allocation will be unblinded to both participants and the study team). For efficiency, research coordinators conducting the home study visit will also be responsible for randomization and measurement of height and weight. Since the study team members will also need to interact with local DPPs, it would be practically challenging to blind the study team members to treatment assignment. The biostatistician will also be unmasked to treatment assignment and will provide required reports to the DSMB. The study team will have real-time access to all systems log data collected by Sweetch in the form of a dashboard.

Considering that hDPPs enroll participants to their programs on a rolling basis depending on the number of interested participants available to join a new cohort and availability of lifestyle coaches, it is possible that there will be times during the enrollment period where there may be an absence of available hDPPs to accept participants randomized to that arm in a timely fashion.

Since the outcomes of this trial are based on time from randomization (and not time from first visit in the hDPP), all efforts will be made to minimize the lag time between randomization and the time to first available hDPP session for a given participant. It is likely that hDPPs will reduce the frequency of new cohort starts during periods of holidays. **To ensure that there is no more than a 4 week lag time from date of randomization to the date of the first available visit for ANY of the hDPPs across the study, randomization will be temporarily suspended until at least one program that offers both in-person and synchronous distance learning has an available start date to accept a hDPP participant within 4 weeks.** While participants will be offered the option of selecting a hDPP (based on distance from home, offerings, and other factors), in the event that the program that they are interested in does not have an available cohort starting until after 4 weeks, participants will be referred to the hDPP with the soonest available start date.

To operationalize referrals to hDPPs, hDPPs will be required to provide the study team an updated schedule of their class sessions and frequency of new cohort enrollment at least quarterly and whenever there is a change in their schedule. Participants will be encouraged to find a program that has an available start date no longer than 8 weeks from the time of enrollment.

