## 3.2 PRIMARY ENDPOINT

The trial is designed as a non-inferiority trial to evaluate whether the Sweetch dDPP is at least as effective as hDPPs on participant attainment of the CDC's benchmark for type 2 diabetes risk reduction, defined as one or more of the following:

- At least 5% weight loss by 12 months
- At least 4% weight loss at 12 months and at least 150 minutes/week of physical activity measured using monthly serial Actigraphy and averaged over months 1-11)
- At least a 0.2% reduction in hemoglobin A1C by 12 months (for participants whose A1C result obtained at baseline study visit is between 5.7% and 6.4%).

Thus, the prospectively defined primary endpoint will be a binary endpoint at 12 months, defined as 1 if at least one of the CDC "success" outcome measures is achieved and 0 if none are achieved. The primary endpoint was selected to align with the current CDC standards for full recognition of DPP programs (effective May, 2021). According to the CDC, participants may demonstrate type 2 diabetes risk reduction by fulfilling one or more of the above outcomes, and, given the broad range of eligibility criteria for the DPP (see Section 5.1), not all DPP participants are eligible to demonstrate success using each of three outcomes in our composite endpoint. Specifically, the A1C change measure can only be used for participants whose baseline measure is in the prediabetic range of 5.7% to 6.4%. These standards require that at least 60% of participants in a given DPP meet the endpoint for attainment of full recognition in order to become a Medicare DPP supplier. The CDC's Standards and Operating Procedures are subject to change during the course of the study. Should the benchmarks for type 2 diabetes risk reduction change prior to completion of the trial, to the extent possible (i.e. assuming we have collected required data during the trial), we will also analyze our outcomes to align with the updated benchmark.

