### 5 STUDY POPULATION

#### 5.1 INCLUSION CRITERIA

In order to be eligible to participate in this study, an individual must meet all of the following criteria:

1. Provision of signed and dated informed consent form
2. Stated willingness to comply with all study procedures and availability for the duration of the study
3. Male or female age 18-75 years
4. Laboratory evidence of prediabetes, defined as *any* of the following lab results, in the *past year*\*:
  - a. Hemoglobin A1C 5.7% to 6.4%
  - b. Fasting glucose 100-125 mg/dl
  - c. Plasma glucose of 140-199 mg/dl measured 2 hours after a 75 gm glucose load
5. Body mass index (BMI)  $\geq 25 \text{ kg/m}^2$  (or  $\geq 23 \text{ kg/m}^2$  for Asians)
6. Proficiency reading English
7. Smartphone user (Android OS 9.0 or iOS 13.3 or newer)
8. Plans to reside in recruitment area for the next 12 months (participant's zip code of residence is within ~45 miles of the study recruitment site )

\*For each of these lab tests, the *most recent* clinically available result for each distinct lab test in the past year will be considered when ascertaining eligibility. These criteria are consistent with participant eligibility criteria for the DPP as defined by the CDC (May 2021 Standards and Operating Procedures).

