### 8.2.2 LABORATORY EVALUATIONS

In this study, we will be using A1C testing for two purposes: a) safety (ruling out diabetes at screening visit) and b) measuring change in A1C (one of the composite endpoints of the study). Considering that some participants could have progressed from prediabetes to diabetes since their last A1C test, a repeat A1C test will be obtained at the screening visit for safety reasons to exclude patients with possible type 2 diabetes (A1C of 6.5% or greater). Such participants will be ineligible to join and will be advised to contact their primary care provider for confirmatory diagnostic testing.

For participants who have not had a laboratory test to confirm the diagnosis of prediabetes as specified in our inclusion criteria (Section 5.1), the POC A1C measurement will be used for screening purposes to ascertain eligibility, and a result between 5.7% and 6.4% would render the participant eligible. For example, if a participant had an A1C result two years ago of 6.2% but has not had a repeated A1C test or fasting glucose in the past year, the screening test would be done to determine prediabetes status.

The second reason for the A1C test will be to determine change in A1C at 6 months and 12 months from the baseline study visit, which is one of the composite endpoints of our study. Of note, the CDC has defined reduction in A1C of 0.2 or more at 1 year to be an indicator of success in the DPP. This outcome measure (a component of our composite endpoint) will be limited to participants whose baseline A1C (obtained by our study team) is between 5.7% and 6.4%.

A1C will be obtained using FDA cleared, CLIA-waived, and NGSP-certified devices (Afinion™ 2 Analyzer, Siemens DCA Vantage, or A1CNow+ test kit). These point-of-care tests require a fingerstick blood sample and an A1C result is obtained in 5 minutes. All A1C testing will be performed by a trained research coordinator.

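### The A1C randomisation strata stop at 5.7%, so eligible participants below that value have no stratum, and the unadjusted primary analysis does not account for their lack of the A1C success route

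*Combined protocol and SAP*

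**What the plan says.** **Randomisation (Section 6.4).** The scheme is "Block stratified randomization by baseline A1C level (5.7% to 6.0% vs. 6.1% to 6.4%) and recruitment site (JHU vs. Reading"). That makes two A1C levels by two sites, or four cells. The section does not say whether baseline A1C means the historical qualifying result or the study-visit measurement.

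**Entry (Section 5.1).** Any one of three results from the past year is enough: an A1C of 5.7 to 6.4%, "Fasting glucose 100-125 mg/dl", or "Plasma glucose of 140-199 mg/dl measured 2 hours after a 75 gm glucose load". Neither glucose route carries a lower limit on A1C.

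**Screening A1C (Section 8.2.2).** A1C is repeated at the visit to "exclude patients with possible type 2 diabetes (A1C of 6.5% or greater"). Only the upper end is closed. A visit A1C of 5.7 to 6.4% is needed for entry only when there is no qualifying laboratory result from the past year.

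**Endpoint (Sections 3.2 and 8.2.2).** Section 3.2 accepts that "not all DPP participants are eligible to demonstrate success using each of three outcomes in our composite endpoint". The A1C route is open only to those whose baseline A1C, as measured by the study team, is 5.7 to 6.4%.

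**Analysis (Sections 9.3, 9.4.5 and 9.4.7).** Primary analyses are unadjusted. Covariate models are prompted by observed differences between the arms, and Section 9.4.5 treats them as supportive.

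**The concern.** The endpoint section provides for participants outside the 5.7 to 6.4% range, but the randomisation section does not. As written, the allocation rule cannot be applied to someone who is eligible with an A1C below 5.7%. No readable text says where that person goes.

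These participants differ in a way that bears on the outcome, because they have two routes to success where others have three. If their numbers differ between arms by chance, the primary comparison absorbs the difference. Neither the strata nor a pre-specified factor in the analysis removes it.

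**Working it through.** **1. The plan's own figure.** Inputs from Section 9.2: 50% success in both arms, 15-point margin, one-sided 5%, 80% power, 25% attrition.

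n per arm = (1.645 + 0.842)² × 2 × 0.5 × 0.5 / 0.15² = 137.4, rounded up to 138. Then 138 / 0.75 = 184.

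Both published figures reproduce. The strata do not enter the formula, so the sample size is unaffected by this point.

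**2. Range allowed against range covered.** With a qualifying test in the past year, any visit A1C below 6.5% is allowed at randomisation. The strata cover 5.7 to 6.4%. Everything below 5.7% is uncovered, at both sites. Read to one decimal, there is no gap between 6.0% and 6.1%. Two kinds of participant fall outside:

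- Those who qualify on glucose and have an A1C below 5.7%.
- If baseline means the study-visit value, as it does for the endpoint, those with a past-year A1C of 5.7 to 6.4% who read below 5.7% at the visit. Section 8.2.2 queries an A1CNow+ reading only when it differs from an A1C of the past 3 months by -0.9 or less, or +0.8 or more. A drop from 5.9% to 5.5%, for example, would pass without a query.

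**3. Size of a chance imbalance.** Let q be the share below 5.7% and d the shortfall in its success rate. The documents give neither, so both are assumed over a range. With 184 per arm and no balancing of this group:

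- SD of the between-arm difference in share = √(2q(1−q)/184)
- Shift at the edge of the 95% range = 1.96 × SD × d

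| q | People of 368 | SD (points) | 95% range (points) | Shift, d = 10 | Shift, d = 20 | Shift, d = 30 |
|---|---|---|---|---|---|---|
| 5% | 18 | 2.3 | ±4.5 | 0.4 | 0.9 | 1.3 |
| 10% | 37 | 3.1 | ±6.1 | 0.6 | 1.2 | 1.8 |
| 20% | 74 | 4.2 | ±8.2 | 0.8 | 1.6 | 2.5 |
| 30% | 110 | 4.8 | ±9.4 | 0.9 | 1.9 | 2.8 |

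**4. Against the trial's sampling error.** At 50% success the standard error of the difference is √(2 × 0.25/184) = 5.2 points. The share of its variance due to this factor is q(1−q)d²/0.25.

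- q = 20%, d = 30: the 1-SD shift is 4.17 × 0.30 = 1.25 points. The variance share is 0.16 × 0.09 / 0.25 = 5.8%. Removing it all would cut the standard error by 1 − √(1 − 0.058), about 3%.
- q = 20%, d = 10: 0.16 × 0.01 / 0.25 = 0.6% of the variance.

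With 138 analysed per arm the standard error is 6.0 points. The SD in step 3 grows in the same proportion, so these shares do not change.

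**The case against.** The strongest reply is that this is ordinary sampling variation. Randomisation within whatever stratum a participant is assigned to remains unbiased, and the unadjusted confidence interval already carries the imbalance. That stands, and step 4 shows that the gain from controlling the factor is small.

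A second reply is that Section 6.4 stratifies because higher A1C predicts progression to diabetes. For that purpose, placing values below 5.7% in the lower stratum would be workable. That is fair, but the plan does not say so, and it would leave access to the A1C route unbalanced. In an open-label trial where home-visit coordinators also randomise, a written rule is better than a choice made at the visit. That last remark is inference; the documents do not show discretionary placement.

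Third, an imbalance would be visible. Section 9.4.3 reports baseline A1C by arm, Sections 9.4.5 and 9.4.7 allow adjusted models, and Section 9.4.8 analyses each component separately. This helps interpretation. However, the adjusted models depend on what is observed, so they do not replace a pre-specified factor.

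Fourth, the Section 11.17 screening flowchart is not in the text available for this review and may show how low readings are handled. It would not alter the strata listed in Section 6.4, but it is a reason not to assert that such participants must be misfiled.

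**Conclusion.** The gap is real and follows from the plan's own rules: the strata do not cover the population that the eligibility criteria admit. The uncovered group also lacks one success route, and the primary analysis takes no account of that. The consequence is modest. Under the assumed ranges, a chance imbalance at the edge of its 95% range shifts the difference by roughly 0.4 to 2.8 points against the 15-point margin. At an assumed 20% share and 30-point deficit, the factor is about 6% of the variance.

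A reader might infer that the comparison is biased, that the type I error is inflated, or that the trial is under-sized. The documents support none of these: allocation stays random within strata, and 138 and 184 per arm reproduce. A reader might also take the 2.5-point cell (20% share, 30-point deficit), one-sixth of the margin, as the expected effect. It is a draw at the edge of the 95% range on top of two assumed inputs. Nor do the documents establish that access to the A1C route strongly affects success. They give no success rate for that route, and Section 3.1.5 notes that few trials have examined A1C reduction in these programmes.

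**What to change.** 1. In Section 6.4, state that the study-visit A1C, the value used for the endpoint, defines the stratum.
2. Add a level below 5.7% to the randomisation list for future enrolment, going from 2 × 2 = 4 cells to 3 × 2 = 6.
3. Pre-specify site and A1C category, including the level below 5.7% (no access to the A1C route), as factors in the primary analysis. Continue to report the treatment effect as a risk difference against the 15-point margin, for example by standardising the fitted probabilities from the logistic model. Amend the statements in Sections 9.3 and 9.4.5 that primary analyses are unadjusted. This step also covers participants already randomised.
4. Report, by arm, how many participants cannot use the A1C route.

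The cost is an updated list and revised wording in the protocol and analysis plan; the sample size stays the same. There are two downsides. The primary analysis is no longer unadjusted, and there are two more small strata. Assuming the same share at both sites and the 35% of recruitment that Section 5.5.11 expects from Reading, the new Reading cell would hold about 18.4 × 0.35 = 6 people at a 5% share and 110.4 × 0.35 = 39 at a 30% share.
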